3.1. Enrollment and Randomization

Due to the prospective nature of this study and the potential for the Decipher test results to materially impact the clinical management of patients participating in the study, all patients must be consented to participate in the study. Eligible patients (Section 4.1) identified by the participating urologist should be consented to discuss the results of the surgical pathology and Decipher results using the Informed Consent Form (ICF).

In the event that the treating urologist decides to terminate a patient's involvement in the study they must notify the sponsor and provide a reason for termination in the electronic case report form.

As described in the preceding section, this is a cluster-randomized trial so individual subjects do not receive a randomized group assignment, but are allocated to the group assigned to the center at the time they enroll.

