2.3. Exploratory Objective

1. To determine whether it is possible that use of GC will result in an overall reduced net cost to the healthcare system by avoiding treatment in many patients.

3. Study Design

This is a 4-5 year (up to 2 years enrollment , 3-year follow-up) prospective, cluster-crossover, unblinded, study of 550 subjects from at least fourteen centers of the Michigan Urological Surgery Improvement Collaborative (MUSIC), a physician-led quality improvement consortium comprised of the vast majority of urology practices within the state of Michigan.

According to the cluster-crossover design, each participating MUSIC clinical center within MUSIC will be randomized to either a Genomic Classifier care-based (GC) or Usual-Care-based (UC) strategy for a period of 3 months, during which all enrolled subjects within the center will be provided the assigned strategy. Random assignments will be generated centrally by a study statistician and provided to centers immediately before commencing enrollment in each 3-month period. The randomization will be based on a random block size of either 2 or 4. This will ensure that each center will have two periods of GC and two periods of UC during the enrollment period, maintaining study-wide balance and blinding of assignments in subsequent periods.

If enrolled during the GC period, both subjects and their treating physician will be provided GC (from GenomeDx) and CAPRA-S (from MUSIC-Central) to inform their treatment plan. In the UC periods, only the CAPRA-S results, provided by MUSIC-Central, will be available. Blinding of subjects and treating physicians will not be possible given the nature of the information.

Subjects enrolled to the GC arm will receive MUSIC-led education about the GC test. The pros and cons of the GC test need to be described by an unbiased clinician scientist including the past history of the test (published studies).

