3.4. Clinical Data Collection

Where available, participating physicians in the study will be asked to provide the following clinicopathologic data in the provided case report form (CRF) for subjects meeting the inclusion criteria below. All data submitted to GenomeDx will utilize a case ID number and will be de-identified by the site prior to submission.

1. Ethnicity
2. Age at radical prostatectomy
3. Pre-operative PSA level: last pre-operative PSA level before radical prostatectomy
4. Lymph node status
5. Clinical and pathological stage
6. Clinical and pathological Gleason score (primary, secondary, and tertiary pattern if available)

7. Surgical margin status
8. Extra-prostatic extension
9. Seminal vesicle invasion
10. All available post-op PSA levels
11. Recommended treatment or management option for the patient after surgery
(detailed by type of treatment recommended)
12. Dates of actual treatments
13. Patient outcome

[figure not shown]

Figure 1: Study flow diagram

[figure not shown]

Figure 2: Patient flow timeline

4. Subject Eligibility

4.1. Inclusion Criteria:

Individuals satisfying all of the following criteria will be eligible to participate.

1. Prostate cancer patients who have undergone radical prostatectomy(RP)
2. PSA <0.1 ng/ml at enrollment
3. At least one of the following:
 - a. pT3 (SVI or EPE), **or**
 - b. Positive Surgical Margins
4. Tumor tissue (FFPE block) available for processing
5. RP within 1 year of enrollment
6. 18 years of age or older

4.2. Exclusion Criteria:

Individuals who satisfy **any** of the following criteria will not be eligible to participate.

1. Have regional or distant metastatic disease
2. Received any radiation or hormone therapy (neo-adjuvant, adjuvant, or salvage)
3. Node positive
4. Subjects who do not have banked specimens

5. Endpoints

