5.1. Primary Endpoint

The Primary Endpoint will be whether the subject receives any adjuvant therapy (radiation and/or hormone therapy). Adjuvant will be defined as preceding BCR (i.e.: PSA \geq 0.2 ng/ml) and within 18 months of RP. Patients must have a PSA within 6 months prior to the receipt of radiotherapy.

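### Enrolment can be timed to a known arm for up to a year after RP, and time from RP to enrolment is missing from the primary and time-to-event models

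*Combined protocol and SAP*

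**What the plan says.** Section 3 randomises each centre to one strategy "for a period of 3 months, during which all enrolled subjects within the center will be provided the assigned strategy". Section 3.1 adds that individual subjects are not randomised; they "are allocated to the group assigned to the center at the time they enroll". The participating urologist identifies them, and Section 3 accepts that neither patient nor physician can be blinded.

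Section 3 describes the concealment of later periods as follows: "Random assignments will be generated centrally by a study statistician and provided to centers immediately before commencing enrollment in each 3-month period". It continues: "The randomization will be based on a random block size of either 2 or 4". The stated result is that "each center will have two periods of GC and two periods of UC during the enrollment period". The section then credits the scheme with "maintaining study-wide balance and blinding of assignments in subsequent periods". The same section allows up to two years of enrolment.

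The entry criterion in Section 4.1 is "RP within 1 year of enrollment", with PSA below 0.1 ng/ml at enrolment; Section 4.2 excludes anyone who has already had radiation or hormone therapy. Section 5.1 counts therapy as adjuvant if it comes before BCR and "within 18 months of RP", so the window starts at surgery and not at enrolment.

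The primary model in Section 7.1 contains arm, arm-by-GC-score, CAPRA-S, and random centre and period effects. Section 7.3 uses a similar formulation for salvage, BCR and metastasis, and includes time since surgery in the QOL ANCOVA.

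**The concern.** When recruitment follows a known allocation, the arms are comparable only if the decision to enrol does not depend on the arm. Here the entry window is as long as four 3-month periods, and the text contains no rule on when to approach an eligible patient, no log of those not enrolled and no planned baseline comparison of the arms. (Figures 1 and 2 could not be read; if the timeline in Figure 2 fixes an approach point, the text should state it.) A urologist or patient who wants the test, or does not want it, can enrol now or wait.

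Two distortions could follow. The arms may differ in how much of the 18-month window is left at entry. They may also differ in risk or inclination to treat, and those who enter late have, by the entry criteria, stayed untreated with a low PSA. The first can be adjusted for with dates the trial must hold anyway; the second can only be limited and monitored. At stake is the comparison with similar patients who were not tested, which is how Section 2.1 words the primary objective, and the arm-level secondary outcomes.

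**Working it through.** **1. The stated 2+2 balance.** Inputs from Section 3: blocks of 2 or 4, four periods. The probabilities of the block sizes are not given; 1/2 each is assumed. Write G for a GC period and U for a UC period.

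- Two blocks of 2 give GUGU, GUUG, UGGU, UGUG, each with probability 1/4.
- One block of 4 gives those four plus GGUU and UUGG, each with probability 1/6.
- Mixture: each of the first four has 1/2 × 1/4 + 1/2 × 1/6 = 5/24; GGUU and UUGG have 1/2 × 1/6 = 1/12 each. Total: 4 × 5/24 + 2 × 1/12 = 1.

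Every sequence has two G and two U, so the plan's figure is reproduced when the blocks exactly fill four periods.

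**2. How well the next arm can be guessed** by someone who knows the rule and the arms so far:

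- Period 2: guess the opposite arm. 1/2 × 1 + 1/2 × 2/3 = 83.3%.
- Period 3: certain if the first two were alike (probability 1/6), otherwise a coin toss. 1/6 × 1 + 5/6 × 1/2 = 58.3%.
- Period 4: fixed by the 2+2 rule, 100%.
- Mean: (83.3 + 58.3 + 100)/3 = 80.6%, against 50% under full concealment.

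Other assumptions give:

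| Assumption | Best guess right, period 2 onward (%) | Mean (%) |
|---|---|---|
| Four periods, blocks of 2 only | 100, 50, 100 | 83.3 |
| Four periods, block of 4 only | 66.7, 66.7, 100 | 77.8 |
| Independent blocks, cut at period 4 | 83.3, 58.3, 91.7 | 77.8 |
| Independent blocks, eight periods (24/3) | 83.3, 58.3, 91.7, 54.2, 87.5, 56.2, 89.6 | 74.4 |

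The third row is an alternative to the 2+2 rule and cannot hold together with it: cutting a block short breaks 2+2 with probability 1/2 × 1/2 × 1/3 = 1/12 per centre.

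**3. Endpoint window left at enrolment** = 18 − months since RP.

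- Entry at month 3: 18 − 3 = 15 months.
- Entry at month 6: 18 − 6 = 12 months, so waiting one period from month 3 costs 3/15 = 20% of what was left.
- Entry at month 12: 18 − 12 = 6 months.

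**4. What each analysis adjusts for** (Sections 7.1 and 7.3):

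| Analysis | CAPRA-S, centre, period | Time since RP |
|---|---|---|
| Primary model | yes | no |
| Secondary Objective 2 model | yes | no |
| Salvage, BCR, metastasis | yes (similar formulation) | no |
| QOL ANCOVA | not stated | yes |
| Cost | none stated | no |

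**5. Which terms are exposed.** The GC score enters the primary model only multiplied by the arm indicator. Hence β2 is the slope of treatment on GC score among GC-arm subjects, and β1 is the arm contrast at a GC score of 0. A shift in who enters the GC arm moves β1 and the predicted probabilities; it does not of itself create a slope.

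**6. Scale of possible distortion (illustration only).** Suppose no true arm effect, base rate m, and a fraction f of would-be-treated patients moving from UC to GC periods. The odds become m(1 − f)/(1 − m) in UC and m(1 + f)/(1 − m) in GC, so the spurious OR is (1 + f)/(1 − f) whatever m is: 1.22 for f = 10%, 1.50 for 20%, 1.86 for 30%. With m = 8% (the Section 7.5 rate for CAPRA-S high-risk patients) and f = 20%, the rates are 6.5% and 9.4%. Movement the other way gives the inverse ORs. Clustering and covariates are ignored, and the documents give no value for f.

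**The case against.** The best defence is that the primary test is not an arm contrast. A reader might infer that selective timing undermines the test of β2. The documents do not support that: the GC result reaches only subjects already enrolled in a GC period, so nobody can time entry on a score not yet known. This stands, with the small reservation that the CAPRA-S slope is shared between the arms.

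It would also be wrong to say that no adjustment is planned. CAPRA-S, centre and period are modelled, and QOL adjusts for time since surgery. Time to salvage runs from randomization (Section 5.2), so the 18-month limit does not shorten it. What is missing is time from RP at entry, which can still differ by arm.

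Nor do the documents say that centres are told the 2+2 rule. Assignments are generated centrally and released period by period; the rule is simply written in the protocol. The guessing rates therefore apply to someone who has read it, and period 3 is near a coin toss. Against this, the open current arm is enough for selective approach even if every later arm were perfectly concealed.

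Finally, some oversight exists. Section 7.2 estimates enrolment by centre and by period, Section 10 has six-monthly review of enrolment and participant characteristics, and Section 3.2 requires balanced education. Bunching of numbers could be noticed. None of these calls for time from RP or case mix by arm, so a change in who enrols could pass unseen. Waiting is also limited by the need to remain untreated with PSA below 0.1, though that is itself a form of selection.

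**Conclusion.** The point holds for the arm-level results and not for the primary hypothesis test. Allocation by enrolment date, an open current arm, a one-year entry window and no approach rule allow entry to be timed, and the remaining endpoint window can range from 15 months (entry at month 3) to 6 (entry at month 12) with no adjustment outside QOL. Exposed are β1, the predicted probabilities, and the salvage, BCR, metastasis and cost comparisons. The documents show an opportunity for bias, not its occurrence or size; the ORs above depend on an assumed f.

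The statement that later assignments stay blinded is too strong for anyone who knows the rule. The 81% mean needs exactly four periods and equally likely block sizes; about 74% is the figure for eight periods with independent blocks. Four periods of 3 months are 12 months, which does not match enrolment of up to two years.

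**What to change.** 1. Add months from RP to enrolment as a covariate in the primary model, the Secondary Objective 2 model and the time-to-event models. Both dates are already needed for eligibility and the endpoint, so no new data are required, and a linear term costs one degree of freedom. It corrects for unequal time left; it does not remove selection on unmeasured factors.
2. Require that each patient be approached at the first visit at which eligibility is met. Tabulate enrolment counts, RP-to-enrolment time and baseline factors by centre, period and arm, with counts of eligible patients not enrolled where MUSIC-central data allow. The cost is slightly less flexibility for sites and one extra table.
3. Keep the block sizes and the 2+2 rule out of what centres receive, correct the blinding statement in Section 3, and reconcile two GC plus two UC periods with enrolment of up to two years. This is a wording change. Withholding the rule does not hide the current arm, so it supplements item 2 and does not replace it.

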3.2. Genomic Classifier Education Procedures

It is important to ensure that physician investigators are familiar with interpreting the test results prior to measuring its impact on their treatment recommendations, a set of pre-study regulatory requirements and study training will precede the initiation of this study.

- An overview of the current use of adjuvant and salvage radiotherapy in MUSIC, of the published data on Decipher, and of the study itself will be presented by the PIs at a collaborative-wide meeting. Each participating practice must be present at this meeting or review this content directly with the PIs. The presentation will include a balanced discussion of the current evidence and interpretation of test results in order to avoid potential bias.
- Each physician must review educational materials provided by GenomeDx Biosciences on the Decipher test
- Patient education materials surrounding the study will be provided by MUSIC to each of the practices for patients to review.

3.3. CAPRA-S and GC Result Reporting

The results of the GenomeDx Decipher® test will be communicated in the form of a test report that will be provided to the ordering physician by FAX and a hardcopy is shipped with UPS. The MUSIC coordinating center will generate a CAPRA-S report for all participating patients that will be provided by FAX or e-mail to each practice. The treating urologist will review the CAPRA-S score with the patient.

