6.1. FFPE Block Selection/Specimen Acquisition

FFPE (formalin fixed paraffin embedded) tissues from RP prostate tumor sample blocks will be collected from patients in both the GC and UC arms for transcriptome-wide expression analysis.

The FFPE block from the RP that exhibits a) highest Gleason Score, AND b) highest percent tumor involvement will be selected for sampling with at least 60% tumor by surface area. The pathologist will mark the H&E slide that will be used to guide punching. The marked area should preferentially sample tumor with the highest Gleason grade (e.g., in a 4+3 lesion, the pattern 4 component should be enriched in the punch specimen). Two (2) X 1.5 mm in diameter punches will be sampled from the RP FFPE block (e.g., using a tissue microarray core device or a disposable punch tool, to be provided by GenomeDx). Each punch will be placed in a separate microfuge tube and stored at 4°C until shipping.

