6.5. GenomeDx Decipher[®] Testing

GenomeDx will extract and purify RNA from submitted tumor specimens. If the sample fails to yield sufficient RNA (at least 100 ng) GenomeDx will request a duplicate specimen from the submitting physician (preferably from a different FFPE block for that patient). GenomeDx will then generate cDNA, amplify, label and hybridize it to oligonucleotide arrays. The Decipher gene signature tested will remain unchanged throughout the course of the study, such that all patients will undergo the identical assay.

GenomeDx will then perform QC on the raw microarray data. Samples that fail array QC will be re-amplified (provided there is sufficient RNA remaining). If there is insufficient RNA or the 2nd amplification fails, the duplicate sample will be extracted. After generation of the array data and QC analysis, GenomeDx will return (on dry ice) RNA or specimen cores not used for amplification to the pathologist or discard appropriately.

7. Statistical Considerations

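### GC results obtained outside the assigned strategy are neither excluded at entry (4.2) nor recorded (3.4), so the contrast with untested men is unprotected

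*Combined protocol and SAP*

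**What the plan says.** **Who gets the score.** Section 3 states: "If enrolled during the GC period, both subjects and their treating physician will be provided GC (from GenomeDx) and CAPRA-S (from MUSIC-Central"). For the other arm: "In the UC periods, only the CAPRA-S results, provided by MUSIC-Central, will be available". Section 3.1 adds that a man belongs to the group his centre holds when he enrols, so he does not change group when the centre crosses over.

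**How results travel.** Under Section 3.3 the Decipher result "will be communicated in the form of a test report that will be provided to the ordering physician by FAX". The same section sends a CAPRA-S report for every participant. Tissue, under Section 6.1, "will be collected from patients in both the GC and UC arms for transcriptome-wide expression analysis". Section 3.1 says that eligible patients "should be consented to discuss the results of the surgical pathology and Decipher results". None of these three places restates the arm limit. None says when UC tissue is assayed or who holds the result.

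**Who may enter.** Section 4.1 requires "RP within 1 year of enrollment". Section 4.2 has four exclusions: metastatic disease, prior treatment ("Received any radiation or hormone therapy (neo-adjuvant, adjuvant, or salvage"), positive nodes, and no banked specimen. None concerns a GC result that already exists.

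**What is recorded.** Section 3.4 lists 13 data items. None captures a GC test done before entry or outside the assigned strategy.

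**The concern.** Objective 2.1 compares GC-informed men with men of similar CAPRA-S score who do not have the test. The comparisons of salvage therapy, BCR and metastasis, quality of life and cost likewise set GC use against non-use. All of them need UC men to lack the score.

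The plan controls what the study itself hands out. It does not deal with scores that arrive by another route: a test done in the year before enrolment, or one ordered outside the study afterwards. A man who already knows his score is in effect GC-informed whichever arm his centre holds, so he adds nothing to the contrast.

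There is also selection. Among men tested before entry, those treated because of the result are removed by 4.2, and those not treated remain eligible. Men who enter with a known high score are therefore ones who have so far gone without treatment, and they can enter either arm. With no data field, the number of such men could not be reported.

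**Working it through.** **1. Time available for an outside result.** Entry is allowed up to 12 months after RP (4.1), and the primary endpoint runs to 18 months after RP (5.1). A prior test thus has up to 12 months in which to occur. Even the latest entrant has 18 − 12 = 6 months of primary window left, against a period length of 3 months. The secondary outcomes run to 3 years.

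**2. Dilution of an arm difference.** Let Δ be the difference between informed and uninformed men.
- Result known before entry, share c in both arms: difference = (1 − c)Δ + c × 0 = (1 − c)Δ.
- Result learned off-arm in UC only, share c: difference = Δ − cΔ = (1 − c)Δ.

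The first line assumes equal shares in the two arms. The second assumes that an informed UC man behaves like a GC-arm man. The sample size needed to keep the same power for such a difference rises by 1/(1 − c)².

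**3. Numbers.** Section 3 plans 550 subjects; an equal split (assumed) gives 550/2 = 275 UC men. The documents give no value for c, so a range is shown.

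| c (assumed) | UC men | Remaining difference | N multiplier |
|---|---|---|---|
| 5% | 0.05 × 275 ≈ 14 | 0.95Δ | 1/0.95² = 1.11 |
| 10% | 0.10 × 275 ≈ 28 | 0.90Δ | 1/0.90² = 1.23 |
| 20% | 0.20 × 275 = 55 | 0.80Δ | 1/0.80² = 1.56 |

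**4. Primary test.** In the Section 7.1 model the score enters only as G × GC, with G = 0 in UC. A UC man's score never enters the beta_2 term. The same holds for beta_4 in Secondary Objective 2.

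To see how this works out, I simulated the 7.1 model at N = 350 with 8 sites (as in Table 1), the site means of 7.5.1, site variance 1, period SD 0.36 and the stated ORs of 1.47, 1.15 and 0.24. The assumptions were: OR 1.47 applies per 0.1 of GC score; GC is beta-distributed with mean 0.40 and SD 0.20; the intercept is −2.8. The fit was a penalised logistic approximation to the mixed model, with 1,500 runs per row. Only disclosure in UC was varied.

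| c in UC | Risk difference, GC > 0.45 | Ratio to c = 0 | Power, beta_2 | Median beta_1 |
|---|---|---|---|---|
| 0 | 0.128 | 1 | 87.9% | −1.43 |
| 10% | 0.120 | 0.94 | 89.0% | −1.43 |
| 25% | 0.097 | 0.76 | 88.5% | −1.47 |
| 50% | 0.065 | 0.51 | 88.5% | −1.52 |
| 100% | −0.002 | about 0 | 86.2% | −1.61 |

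The risk difference follows (1 − c) closely, while power for beta_2 stays at 86–89%. The coefficient beta_1 is affected too, but not by shrinking. It is the arm log odds ratio at a GC score of zero against the average UC man, so it drifts as the UC treatment rate changes. The (1 − c) rule applies to differences between arms, not to beta_1 read alone.

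**5. The plan's own figures.** The site ICC reproduces: 1/(1 + π²/3) = 0.233, against the stated 23%. The 83% power at N = 350 can be neither confirmed nor refuted, because the GC distribution, the intercept and the unit of OR 1.47 are not given; plausible choices gave 54% to 97%. The simulated treatment rate in the table was about 16% at c = 0. The only rate given is about 8%, for CAPRA-S high-risk men. The table therefore shows the pattern and does not forecast values.

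**6. Not simulated.** Men with a known high score who have gone untreated can also enter the GC arm. That would tend to lower the treatment rate at high scores there, and so weaken the beta_2 slope. The size cannot be given without the share of such men.

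**The case against.** A reader might infer something stronger: that UC specimens go through the assay, that 3.3 then faxes the score to the urologist, and that the UC arm is not kept free of the score at all. The documents do not support that.

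- Section 3 states who receives GC and ties it to the period of enrolment. With 3.1, a UC man stays a UC man after his centre crosses over.
- Section 3.3 contrasts a CAPRA-S report for all participants with a Decipher report for the ordering physician. Read with Section 3, the second is naturally limited to GC men, although the text does not say so and the requisition in 6.3 carries no arm condition.
- The phrase in 6.5, "such that all patients will undergo the identical assay", follows from a statement that the signature will not change during the study. It concerns assay consistency, not release to UC sites.
- Section 10 requires review of protocol deviations at least every six months. Releasing a UC score against Section 3 would be such a deviation.
- The flow figures and consent form are not available and may cover release; nothing can be held against the plan on that account.

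All of this stands, and it reduces the silence in 3.3 and 6.5 to a matter of consistency. It is also true that c is unknown and that the confirmatory test is nearly immune to disclosure in UC. None of it reaches the remaining gap: enrolling a man with a known GC result follows 4.2 exactly as written, so it is not a deviation, and 3.4 would not record it.

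**Conclusion.** The point holds in a limited form. The UC restriction exists and follows the subject, but the plan does not protect it from GC results obtained before entry or outside the assigned arm.

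The consequence falls on direct comparisons between arms: objective 2.1 against untested men, and the salvage, BCR and metastasis, quality-of-life and cost outcomes. These shrink to about (1 − c) of their true size, for example 0.90Δ at an assumed 10%. The coefficient beta_1 is distorted rather than simply shrunk.

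The beta_2 test hardly reacts to disclosure in UC under the assumptions above. This works both ways: beta_2 could be significant while the comparison with untested men is diluted unseen. Selection of untreated men with known high scores into the GC arm could weaken beta_2, by an amount that cannot be sized here. How much any of this matters depends on c, which the documents do not give and which the trial as planned would not measure.

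**What to change.** 1. **Section 4.2:** add an exclusion for men in whom a genomic classifier result for this tumour is already known to the patient or treating physician.
2. **Section 3.4:** add one item for the date and result of any GC test known outside the assigned strategy, before or after enrolment.
3. **Section 7:** keep the analysis by assigned arm and report the number and share of such men by arm. As a sensitivity analysis, repeat the arm comparisons without men whose result was known before enrolment; this is a baseline feature and can be removed from both arms alike. For results learned later, do not drop the men; show the arm difference rescaled by 1/(1 − c) with the observed c.
4. **Sections 3.3 and 6.5:** for consistency with Section 3, state that Decipher reports go only to physicians of subjects enrolled in a GC period, and that any UC assay result is not released to sites before that subject's primary endpoint is recorded.

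The cost is a few men lost to the exclusion, one extra CRF item and short wording changes. Deferring all UC assays and withholding scores for the full 3 years would be a heavier and more debatable change, and this point does not require it.
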